8.3.1 General management in both groups

From inclusion up to day of extubation (and not reintubated within 48h after extubation), ventilation settings will be adjusted by the attending physician or respiratory therapist. Subject condition, sedation, analgesic and vasopressor use, and one blood gas analysis will be collected twice a day if blood gas analysis is done routinely by the ICU department, otherwise ventilation parameters will only be collected.

Subjects will be monitored by the attending physicians and all ventilation variables will be continuously recorded from inclusion to extubation or death. Except for ventilation, all other procedures and care (sedation, hemodynamics, glycemic control, etc.) will be conducted according to the protocols of the site by the subject's attending physicians.

Data listed below will be captured in the eCRF:

- Intubation/reintubation status
- INTELLIVENT-ASV randomization violation status
- Vitals signs: Blood pressure, pulse rate and temperature;
- Acute pulmonary condition;
- 24h Recording of ventilation parameters (Memory Box)

- Ventilation settings
- All concomitant medications including sedation;
- SOFA will be repeated at day 3 and 7, in order to follow the evolution of organ failure.
- Memory Box recording
- Blood gas analysis
- Severity scores based on the most abnormal values in oxygenation and laboratory results in the last 24h period (day 0):
 - Simplified Acute Physiology Score (SAPS II)
 - Acute Physiology and Chronic Health Evaluation (APACHE II)
 - SOFA score
- Concomitant sedation, analgesia and myorelaxants use
- Concomitant vasopressors and inotropics use
- Number of recruitment movers within the last observation period
- Concomitant rescue therapies (proning, Nitric oxyde, ...)
- Weaning information associated interventions (Patient Passive/Active but still on MV, NIV, CPAP, High Flow.)
- Advers Event collection

Recorded data has to be 24 hours at minimum and 80% of the invasive ventilation duration within the allocated randomized ventilation mode have to be recorded in the in Memory Box.

If the subject's medical condition requires medical intervention (bronchoscopy, trancescopy, radiology or OR interventions...etc) and the subject is allocated to the INTELLiVENT-ASV arm, the allocated randomized ventilation mode may be switched off for the required time period. This needs to be documented in the subject's medical chart.

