Dropout could occur when patients are ventilated for less than 24 hours after inclusion because of unexpected death, transfer to another ICU, or withdrawal of informed consent. We expect a maximum of 5% of these cases. Note a maximum of 5% of subjects are anticipated for which not 80% of mechanical ventilation time could be recorded within the allocated randomized ventilation mode due to documented technical reason. The recorded data will be used (with 'percent spent' calculated per the recorded time) for the primary analysis of the co-primary endpoints. As a sensitivity analysis, these values will be treated as missing data.

If the ventilation mode is modified by the site personnel by oversight or lack of training (deviating from the allocated randomization arm) and the subject's medical condition did not require it, the ventilation mode should be set back to allocated randomization arm. A protocol deviation and the event will be recorded in the eCRF accordingly.

If the site's principal investigator determines that the study is no longer in the subject's best interest (including the randomized ventilation mode) the subject's ventilation and study data collection ends. The site needs to complete an AE and the End of Study eCRF.

A. Gas exchanges targets:

SpO₂ will be kept in the ranges:

- 94 - 98% for normal lung, mild and moderate ARDS, and brain injured subjects
- 90-96% for moderate ARDS
- 88 - 95% for severe ARDS
- 90 - 94% for COPD without chronic hypoxemia or hypercapnia
- 88 - 92% for chronic hypercapnic subjects or subjects on long term oxygen

PaCO₂ will be kept in the range:

- 35 - 40 mm Hg for brain injury
- 35 - 50 mm Hg for normal lung, mild and moderate ARDS, COPD subjects without chronic hypercapnia
- ≥ 50 mm Hg in severe ARDS, severe COPD, and subjects with chronic hypercapnia if pH > 7.25

B. Passive subjects:

i. Ventilator settings:

Tidal volume will be kept in the range:

- 6-10 mL/Kg IBW for normal lung subjects, brain injury, and COPD subjects
- 4-8 mL/Kg IBW for ARDS

ii. Lung protection monitoring:

Plateau pressure will be measured at least twice a day and kept below 30 cmH₂O. Driving pressure will be measured at least four times a day and kept below 15 cmH₂O in all subjects.

In ARDS subjects, Plateau pressure between 30 and 35 cmH₂O will be accepted if driving pressure remains below 15 cmH₂O.

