If plateau pressure exceeds 35 cmH₂O or driving pressure exceeds 15 cmH₂O, tidal volume will be decreased by 1 mL/Kg IBW keeping it above 4 mL/Kg or inspiratory pressure will be decreased by 2 cmH₂O.

iii. Additional and rescue procedures:

Continuous myorelaxant infusion, repeated recruitment maneuvers, nitric oxide, and prone position will be considered as additional procedures at the clinician's discretion.

If PaO₂ ≥ 55 mmHg or SpO₂ ≥ 88% with FIO₂ of 1.0 cannot be maintained, clinicians may employ rescue procedures. APRV, high frequency ventilation, ECCO2R and ECMO will be considered as a rescue therapies. The subjects will continue to be followed and included in the analysis on an intention-to-treat basis. Failure of the protocol and subsequent need for rescue therapy will constitute a secondary outcome. Control group subjects will not be allowed to cross-over to the INTELLiVENT-ASV group.

C. Spontaneous breathing subjects:

i. Ventilator settings:

Ventilation support will be adjusted to keep tidal volume in the range:

- 6-10 mL/Kg IBW for normal lung subjects, brain injury, and COPD subjects

- 4-8 mL/Kg IBW for ARDS

Ventilation support will be adjusted to keep respiratory rate \leq 35 Breaths/min.

Inspiratory trigger settings will be set between 1 and 5 L/min or 0.5 and 2 cmH₂O or activate Intellisync+.

Expiratory trigger setting will be set between 10 and 80% of the maximal inspiratory flow or activate Intellisync+.

Pressure rise time will be set between 0 and 400 ms.

Automated tube compensation if appropriate.

D. Weaning:

The INTELLiVENT-ASV or control arm ventilator protocols will be continued until subjects are able to breathe unassisted for 48 hours, death, ICU discharge, study withdrawal, if the site's principal investigator determines that the study is no longer in the subject's best interest or day 28, whichever comes first.

i. Screening of readiness to wean criteria

A screening of readiness to wean criteria will be performed twice a day between 6h00 and 18h00 for all subjects mechanically ventilated for more than 24h.

ii. Extubation

After a successful weaning trial, extubation criteria will be assessed:

- Coma Glasgow Score > 8
- Ability to cough
- Ability to swallow
- Absence of severe upper airway obstruction
- Successful cuff leak test

If all these criteria are fulfilled, subject will be extubated within 12 hours after the successful weaning trial.

iii. Ventilation management after extubation

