8.3.2 Ventilation protocol in non-automated ventilation group

In order to standardize the non-automated ventilation process, Investigators will aim to keep the control arm (conventional non-automated ventilator) as close to the standard of care of the participating sites as possible.

General approach: The overall goals for the control arm ventilation protocol will be similar to those in the INTELLIVENT-ASV group including all recommendation available regarding gas exchanges targets, ventilator settings, protective ventilation targets, and weaning management (16, 32).

A. Passive subjects:

i. Ventilation mode

Any controlled mode will be possible such as volume control (CMV), pressure control (P-CMV), dual mode (APVcmv and APVsimmv), DuoPAP, SIMV, and P-SIMV. APRV will not be accepted. Tube resistance compensation (TRC) can be added.

ii. Ventilator settings

Respiratory rate will be adjusted according to PaCO_2 with a maximum of 35 Breaths/min.

Table 2: Management of pH and PaCO_2 :

$\text{pH} < 7.15$	$\text{pH}= 7.15 - 7.29$	$\text{pH}= 7.29 - 7.45$	$\text{pH} > 7.45$
Increase Respiratory rate up to 35 b/min and keep $\text{PaCO}_2 > 25$ mm Hg	Increase Respiratory rate up to 35 b/min and keep $\text{PaCO}_2 > 25$ mm Hg	Maintain VT around 6 mL/kg IBW in ARDS subjects and between 6 – 8 mL/Kg IBW for other subjects and maintain respiratory rate below 35 b/min.	Decrease respiratory rate but not below 6 /min
Consider NaHCO_3 If needed increase VT by 1 ml/Kg IBW or increase P_{INSP} by 2 cmH ₂ O with a maximum VT at 8 mL/Kg IBW for ARDS subjects and 10 mL/Kg IBW for other subjects. P_{PLAT} can be higher than 35 cmH ₂ O in case of extreme acidosis.	Consider NaHCO_3 If needed increase VT by 1 ml/Kg IBW or increase P_{INSP} by 2 cmH ₂ O with a maximum VT at 8 mL/Kg IBW for ARDS subjects and 10 mL/Kg IBW for other subjects. Keep $P_{\text{PLAT}} \leq 35$ cmH ₂ O.	Consider NaHCO_3 If needed increase VT by 1 ml/Kg IBW or increase P_{INSP} by 2 cmH ₂ O with a maximum VT at 8 mL/Kg IBW for ARDS subjects and 10 mL/Kg IBW for other subjects. Keep $P_{\text{PLAT}} \leq 35$ cmH ₂ O.	Consider NaHCO_3 If needed decrease VT by 1 ml/Kg IBW or decrease P_{INSP} by 2 cmH ₂ O with a minimum VT at 4 mL/Kg IBW for ARDS subjects and 5 mL/Kg IBW for other subjects.

PEEP will be set using PEEP/FiO₂ table, PEEP trial or transpulmonary pressure (based on the local hospital protocol).

PEEP will be kept in the range:

- 5-10 cmH₂O for normal lung subjects and COPD

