8.3.3 Ventilation protocol in INTELLiVENT-ASV ventilation group

Subject allocated to INTELLiVENT-ASV group will be ventilated with this mode from inclusion to the end of the study. Tube resistance compensation (TRC) can be added.

A. Passive subjects:

i. Ventilator settings:

Clinician will set the IBW, subject condition, PetCO₂ and SpO₂ targets, PEEP ranges, and alarms and activate the controllers. The minimal FiO₂ will be set at 0.21. An arterial blood gas will be performed 30-60 min later in order to adjust the PetCO₂ target.

Table 3: Management of pH and PaCO₂:

pH < 7.15	pH= 7.15 – 7.29	pH= 7.29 – 7.45	pH > 7.45
Decrease PetCO ₂ targets by 5 mm Hg and keep PaCO ₂ > 25 mm Hg	Decrease PetCO ₂ targets by 5 mm Hg and keep PaCO ₂ > 25 mm Hg	No change	Increase PetCO ₂ targets by 5 mm Hg
Consider NaHCO ₃	Consider NaHCO ₃		

ii. Controller deactivation

PEEP and FiO₂ controller will be transiently deactivated if it is not possible to get a good SpO₂ signal with both finger and ear sensors. SpO₂ signal quality will then be re-assessed every 6h in order to restart oxygenation controller as soon as possible.

PEEP controller is by design deactivated when brain injury and chronic hypercapnia conditions are selected. PEEP will be set manually as in the non-automated ventilation group.

PEEP controller will not be deactivated in normal and ARDS conditions. Clinician can adjust PEEP ranges and use very narrow ranges if it is clinically needed.

Ventilation controller will be de-activated only if the clinical condition needs a %MV below 70% or above 200%.

Reasons and duration of controllers de-activation will be recorded in the eCRF.

B. Spontaneous breathing subjects:

i. Ventilator settings:

Clinician will set the IBW, subject condition, PetCO₂ and SpO₂ targets, PEEP ranges, and alarms and activate the controllers. The minimal FiO₂ will be set at 0.21. An arterial blood gas will be performed 30-60 min later in order to adjust the PetCO₂ target.

PEEP will be kept in the range:

- 5-10 cmH₂O for normal lung subjects and COPD
- 5-15 cmH₂O for ARDS and obese subjects

C. Weaning:

Weaning in the INTELLiVENT-ASV group will use quick wean function.

i. Quick wean activation

Quick wean will be activated when subject is stabilized with absence or minimum doses of sedation and vasopressor.

If subject has a coma Glasgow score above 8, quick wean function will be activated with SBT.

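### For passive control-arm subjects, Section 8.3.1 B.ii orders a decrease in tidal volume or pressure where Table 2 permits an increase, their plateau-pressure limits differ, and neither passage says which prevails

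*Protocol*

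**What the plan says.** Protocol Section 8.3.1 is headed "General management in both groups", and its part B covers passive subjects. Under lung protection monitoring (B.ii) it sets:

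- a plateau target: "Plateau pressure will be measured at least twice a day and kept below 30" cmH2O;
- a driving-pressure target for all subjects: "Driving pressure will be measured at least four times a day and kept below 15" cmH2O;
- a tolerance: "In ARDS subjects, Plateau pressure between 30 and 35" cmH2O is accepted while driving pressure stays under 15;
- an action rule: "If plateau pressure exceeds 35" cmH2O, or driving pressure exceeds 15, then "tidal volume will be decreased by 1 mL/Kg IBW keeping it above 4 mL/Kg", or inspiratory pressure is lowered by 2 cmH2O. No pH exception is given.

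Table 2 in Section 8.3.2 applies to passive control-arm subjects. As printed, its three columns up to pH 7.45 each contain "If needed increase VT by 1 ml/Kg IBW", or a 2 cmH2O rise in inspiratory pressure. The tidal-volume ceiling is 8 mL/kg in ARDS and 10 mL/kg otherwise. The columns for pH 7.15 to 7.29 and 7.29 to 7.45 cap plateau at 35 for every condition. The column below 7.15 lets plateau go above 35. Table 2 does not mention driving pressure.

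Neither passage refers to the other. Table 6 (Section 10.4.5) scores Pmax, and Pmax minus PEEP in passive ARDS. The primary safety endpoint is the percentage of time with at least one variable sub-optimal.

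**The concern.** Section 8.3.2 says it aims to standardise non-automated ventilation. Yet the general rule and the control-arm table give different directions for the same acidotic subject with high driving pressure, and different plateau limits for the same non-ARDS subject. Two sites can each point to a protocol passage while moving settings in opposite directions.

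Two things are at stake. Bedside staff caring for critically ill subjects lack one clear instruction. And a scored component of a co-primary endpoint is delivered in the comparator arm under rules that do not agree, in a trial where staff know the allocation.

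**Working it through.** The plan gives no figure to reproduce, so the check sets the rules side by side.

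**(a) Driving pressure above 15, plateau at most 35, pH up to 7.45.** Example: passive control subject with ARDS, pH 7.20, plateau 28, driving pressure 16.

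- 8.3.1: 16 > 15, so decrease: VT −1 mL/kg, or inspiratory pressure −2 cmH2O.
- Table 2, column 7.15 to 7.29: plateau 28 ≤ 35, so an increase is permitted if needed: VT +1 mL/kg, or inspiratory pressure +2 cmH2O.
- Gap after one step: (+1) − (−1) = 2 mL/kg, or (+2) − (−2) = 4 cmH2O.

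The clash is plainest below pH 7.29. The 7.29 to 7.45 column first asks for tidal volume to be maintained, then prints the same permission.

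**(b) Non-ARDS subjects, plateau from 30 to 35.** 8.3.1 keeps plateau below 30. Table 2 caps it at 35 with no distinction by condition.

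**(c) Plateau above 35.** 8.3.1 orders a decrease. Table 2 permits the higher plateau below pH 7.15. At pH 7.15 to 7.45 the two agree, because Table 2 also requires at most 35.

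**Grid.** Crossing 4 conditions, 4 pH columns, plateau {28, 32, 36} and driving pressure {12, 16, 19} gives 4 × 4 × 3 × 3 = 144 passive control-arm states. The table counts those where 8.3.1 orders a decrease and Table 2 permits an increase. Scoring assumes Pmax ≥ plateau and Pmax − PEEP ≥ driving pressure.

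| pH column | Opposed | Plateau ≤ 35 | Plateau > 35 | Sub-optimal in Table 6 |
|---|---|---|---|---|
| < 7.15 | 28 | 16 | 12 | 18 |
| 7.15–7.29 | 16 | 16 | 0 | 6 |
| 7.29–7.45 | 16 | 16 | 0 | 6 |
| > 7.45 | 0 | 0 | 0 | 0 |
| Total | 60 | 48 | 12 | 30 |

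The 48 arise only through driving pressure, which Table 2 ignores. In 9 further non-ARDS states (plateau 32, driving pressure 12) no decrease is triggered, but Table 2 permits a plateau that 8.3.1 keeps below 30.

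These counts test the wording and are not patient frequencies. The grid varies plateau and driving pressure independently. Taking driving pressure as plateau minus PEEP, the 9 further states imply PEEP 32 − 12 = 20, outside the 5–10 range that 8.3.2 sets for normal lung and COPD (it gives none for brain injury). With PEEP at most 10, a plateau above 30 means driving pressure above 30 − 10 = 20, so in those subjects (b) arises together with (a). The example in (a) implies PEEP 28 − 16 = 12, inside the 5–25 range for ARDS.

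**Link to the endpoint.** In passive subjects, Table 6 scores Pmax as sub-optimal above 30 in normal lung and brain injury, and above 35 in ARDS and chronic hypercapnia. If Pmax ≥ plateau, time at plateau above 30 and up to 35 is sub-optimal in the first two conditions. With Pmax in that same band, ARDS and chronic hypercapnia score only acceptable on Pmax. In passive ARDS, Pmax minus PEEP of 18 or more is sub-optimal: taking Pmax as about plateau, the subject in (a) starts at 16 and reaches 16 + 2 = 18 after one upward pressure step.

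**The case against.** The best defence is that 8.3.1 is mandatory and Table 2 permissive. A site satisfies both by not using the permission, and 8.3.2 says control-arm goals include protective targets similar to those of the other arm. This softens (a). It does not settle it, because Table 2 states its own plateau limits, different from those in 8.3.1, so it cannot be read as simply inheriting them.

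A reader might count three unrelated plateau limits. Much of that is tiering: target below 30, ARDS tolerance to 35, action above 35. Nor does a non-ARDS subject at plateau 33 escape 8.3.1, since the target is itself an instruction. What remains is below 30 against up to 35 outside ARDS, and decrease against permission above 35. The sentence for pH below 7.15 may well be an intended exception, but 8.3.1 does not mention it and it does not cover driving pressure.

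A reader might also infer that only the control arm is allowed into penalised ranges, which would inflate the device's safety benefit. The documents do not support that. In the INTELLiVENT-ASV arm, "An arterial blood gas will be performed 30-60 min later in order to adjust the PetCO₂ target", and Table 3 lowers that target by 5 mm Hg in acidosis. The device then adjusts ventilation to PetCO2 in passive subjects (Section 3), within a clinician-chosen inspiratory-pressure limit, so ventilation can rise there too.

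Finally, a reader might think that Table 2's tidal-volume steps reach the high sub-optimal tidal-volume range. They cannot: the ceilings are 8 and 10 mL/kg, and Table 6 scores passive tidal volume as sub-optimal only above 10, or above 12 in chronic hypercapnia.

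**Conclusion.** The contradiction stands in a limited form: passive control-arm subjects, at (a), (b) and (c), with no precedence stated. Its demonstrable size is a gap of 2 mL/kg or 4 cmH2O after one step under each rule, and a plateau band above 30 and up to 35 that Table 2 allows and that counts as sub-optimal time in normal-lung and brain-injury subjects.

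The scoring link assumes Pmax is at least plateau, since plateau itself is not scored. The endpoint is a continuous percentage of time, so entering a sub-optimal range adds time rather than recording a failure. The documents do not say how often these states occur, so neither the direction nor the size of any between-arm bias can be established. The case for action rests on conflicting bedside instructions and inconsistent delivery of the comparator.

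**What to change.** The sponsor and investigators should reconcile Section 8.3.1 B.ii with Table 2, state which passage takes precedence when pH and pressure limits conflict (including whether the sentence for pH below 7.15 is an exception to 8.3.1), and confirm that the 8.3.1 limits apply in both arms, since Table 3 does not restate them. The clinical content is theirs to decide.

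The cost is a protocol amendment to one section and one table, the approvals that Section 11.9 requires before implementation, and a memo to the approximately twenty sites. No new procedures or data are needed.

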8.3.2 Ventilation protocol in non-automated ventilation group

In order to standardize the non-automated ventilation process, Investigators will aim to keep the control arm (conventional non-automated ventilator) as close to the standard of care of the participating sites as possible.

General approach: The overall goals for the control arm ventilation protocol will be similar to those in the INTELLIVENT-ASV group including all recommendation available regarding gas exchanges targets, ventilator settings, protective ventilation targets, and weaning management (16, 32).

A. Passive subjects:

i. Ventilation mode

Any controlled mode will be possible such as volume control (CMV), pressure control (P-CMV), dual mode (APVcmv and APVsimmv), DuoPAP, SIMV, and P-SIMV. APRV will not be accepted. Tube resistance compensation (TRC) can be added.

ii. Ventilator settings

Respiratory rate will be adjusted according to PaCO_2 with a maximum of 35 Breaths/min.

Table 2: Management of pH and PaCO_2 :

$\text{pH} < 7.15$	$\text{pH}= 7.15 - 7.29$	$\text{pH}= 7.29 - 7.45$	$\text{pH} > 7.45$
Increase Respiratory rate up to 35 b/min and keep $\text{PaCO}_2 > 25$ mm Hg	Increase Respiratory rate up to 35 b/min and keep $\text{PaCO}_2 > 25$ mm Hg	Maintain VT around 6 mL/kg IBW in ARDS subjects and between 6 – 8 mL/Kg IBW for other subjects and maintain respiratory rate below 35 b/min.	Decrease respiratory rate but not below 6 /min
Consider NaHCO_3 If needed increase VT by 1 ml/Kg IBW or increase P_{INSP} by 2 cmH ₂ O with a maximum VT at 8 mL/Kg IBW for ARDS subjects and 10 mL/Kg IBW for other subjects. P_{PLAT} can be higher than 35 cmH ₂ O in case of extreme acidosis.	Consider NaHCO_3 If needed increase VT by 1 ml/Kg IBW or increase P_{INSP} by 2 cmH ₂ O with a maximum VT at 8 mL/Kg IBW for ARDS subjects and 10 mL/Kg IBW for other subjects. Keep $P_{\text{PLAT}} \leq 35$ cmH ₂ O.	Consider NaHCO_3 If needed increase VT by 1 ml/Kg IBW or increase P_{INSP} by 2 cmH ₂ O with a maximum VT at 8 mL/Kg IBW for ARDS subjects and 10 mL/Kg IBW for other subjects. Keep $P_{\text{PLAT}} \leq 35$ cmH ₂ O.	Consider NaHCO_3 If needed decrease VT by 1 ml/Kg IBW or decrease P_{INSP} by 2 cmH ₂ O with a minimum VT at 4 mL/Kg IBW for ARDS subjects and 5 mL/Kg IBW for other subjects.

PEEP will be set using PEEP/FiO₂ table, PEEP trial or transpulmonary pressure (based on the local hospital protocol).

PEEP will be kept in the range:

- 5-10 cmH₂O for normal lung subjects and COPD
- 5-25 cmH₂O for ARDS subjects
- 5-15 cmH₂O for obese subjects

FiO₂ will be adjusted to the lowest to achieve SpO₂ target.

B. Spontaneous breathing subjects:

i. Ventilation mode:

Any assisted and spontaneous mode will be possible such as pressure support (SPONT), volume support (VS), SIMV, P-SIMV, and DuoPAP. APRV will not be accepted.

ii. Ventilator settings:

Ventilation support will be adjusted to keep tidal volume in the range:

- 6-10 mL/Kg IBW for normal lung subjects, brain injury, and COPD subjects
- 4-8 mL/Kg IBW for ARDS

Ventilation support will be adjusted to keep respiratory rate ≤ 35 Breaths/min.

PEEP will be kept in the range:

- 5-10 cmH₂O for normal lung subjects and COPD
- 5-15 cmH₂O for ARDS and obese subjects

C. Weaning

The INTELLiVENT-ASV or control arm ventilator protocols will be continued until subjects are able to breathe unassisted for 48 hours, death, ICU discharge, study withdrawal, the Principal investigator of the site determines that the study is no longer in the subject's best interest or day 28, whichever comes first.

i. Weaning trial

When the readiness to wean criteria will be fulfilled, a weaning trial will be performed on the same day for a duration of 30 min by any method with PEEP ≤ 5 cmH₂O and PS ≤ 7 cmH₂O: CPAP, tube compensation, minimal pressure support, T tube, or tracheostomy mask.

